13.6 Multiple End Points and Multiple Comparisons

Duration of Effect, as assessed by PPT and QST Heat are co-primary efficacy parameters. In order to control the overall significance level for the two primary endpoints, the total alpha level of 0.1 is Bonferroni adjusted to $0.10/2 = 0.05$ (since this is a proof of concept study, the total alpha level of 0.1 instead of 0.05 has been selected). The study will be considered successful if either of the two primary endpoints is statistically significant.

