mean Heat sensation threshold of 48.5°C or less, based on the last 2 of the 3 readings. Post-Baseline, the presence of analgesia/anesthesia will be defined when the heat sensation threshold at the treated site is higher than the Baseline (“Responder”).

All tests on the treated cheek will be done near the center of the circumscribed area, but in a slightly different place at each consecutive evaluation time point. All tests on the non-treated cheek will be performed at approximately the same part of the cheek as those on treated cheek.

Randomization: A randomization code will determine the sequence of treatments and to which circumscribed area the treatment is administered (left or right cheek). Sensory testing will be done in the following order: pin prick followed, where applicable, immediately by heat sensation tolerance.

Subjects retain the right to withdraw from the study at any time.

EFFICACY MEASUREMENTS

The primary comparison of interest is one spray of CTY-5339-A compared to one spray of CTY-5339-CB. Co-primary efficacy variables are duration of effect as determined by PPT and duration of effect as measured by QST Heat. Duration of effect is defined as the time (in minutes) from onset to treatment failure (for PPT, treatment failure occurs when an assessment of “Same/More” pain, and for QST, a treatment failure occurs when the average heat temperature is the same or less than the average heat temperature at Baseline up to the 60-minute time point (at two consecutive time points).

The secondary efficacy variables include:

- Duration of anesthesia (PPT and QST Heat) for the two sprays of CTY-5339-A compared to one spray of CTY-5339-CB plus CTY-5339-P
- Duration of anesthesia (PPT and QST Heat) for the two sprays of CTY-5339-A compared to one spray of CTY-5339-A
- Onset of anesthesia for PPT and QST Heat
- Percentage of responders for PPT and QST Heat for both onset and duration
- Percentage of responders for PPT and QST Heat at each time point

OTHER MEASUREMENTS

At Baseline and at the end of the 60-minute test session an ECG, vital signs, and a 7 mL blood draw will be taken. The blood will be analyzed for the occurrence of subclinical methemoglobinemia by the HUP – Pepper Lab via co-oximetry analysis. At screening and throughout each test session, subjects will also be monitored with pulse oximetry. Methemoglobinemia is being defined as >5% of a subject’s

hemoglobin in the methemoglobin state, or a pulse oximetry reading of less than 91%.

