ESTIMATED DURATION OF SUBJECT PARTICIPATION IN THE STUDY:

The subjects will be tested on two separate occasions. Each session will take approximately two hours total time; however, the actual efficacy testing will take 60 minutes. There will be 4-14 days spacing between visits. A phone follow-up will occur 3 days (\pm 1 day) and 15 days (\pm 2 days) after the subject completes Sessions 1 and 2, respectively. If there are any adverse side effects, at the discretion of the PI, the subject may be asked to return to the study site for evaluation.

DURATION OF STUDY:

The study will be completed when the last subject completes the last follow up phone call. The expectation is that the study will be completed within 4-6 months of the first subject entry.

NUMBER OF SUBJECTS:

Up to 150 male and female subjects will be screened in order to enroll up to 76 ASA Category I or II subjects. The total number of exposures to study medication will be 152 (76 subjects x 2 exposures). Each of the CTY-5339-A treatment regimens will have 38 exposures and the CTY-5339-CB will have 76 exposures.

SAMPLE SIZE DETERMINATION:

The sample size was selected based on evaluating a reasonable number of subjects to determine whether CTY-5339-A has a longer duration of action than CTY-5339-CB, which contains 14.0% benzocaine only.

DOSAGE:

(specific gravity is slightly less than 1; therefore 200 μ L is an approximate volume.)

CTY-5339-A 1-metered spay = 200 mg total (\approx 200 μ L)
Benzocaine 28 mg + Tetracaine HCl 4 mg

CTY-5339-A 2-metered spays = 400 mg total (\approx 400 μ L)
Benzocaine 56 mg + Tetracaine HCl 8 mg

CTY-5339-CB = 200 mg (\approx 200 μ L)
Benzocaine 28 mg

INCLUSION CRITERIA:

- a. Male and female subjects between 18-75 years of age with a Body Mass Index (BMI) \leq 32;
- b. Subjects are ASA Category I or II and are in good physical health as judged by physical and laboratory examinations;
- c. Subjects with normal appearance of the oral mucosal tissues;
- d. At screening and at Baseline during Session 1, subjects with PPT scores on both cheeks of at least "3" (on a 10 point NRS) on the last 2 of 3 readings, 1 of which must be a score of at least "4";
- e. Subjects with mean QST Heat sensation temperature assessments

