8.4 Hypothesis

The following hypotheses will be tested to analyze the primary outcomes of the study:

- The null hypothesis that the duration of anesthesia (PPT and QST Heat) for the one spray CTY-5339-A group is the same as the corresponding duration for the CTY-5339-CB one spray group will be tested against the alternative hypothesis that the means are not equal.

The following hypotheses will be tested to analyze the secondary outcomes of the study:

- The null hypothesis that the duration of anesthesia (PPT and QST Heat) for the two spray CTY-5339-A group is the same as the corresponding duration for the CTY-5339-CB one spray plus CTY-5339-P one spray group will be tested against the alternative hypothesis that the means are not equal.
- The null hypothesis that the onset of anesthesia (PPT and QST Heat) for the CTY-5339-A groups is equal to the corresponding onset for CTY-5339-CB group will be tested against the alternative hypothesis that the means are not equal.
- The null hypothesis that the onset time until the first responder event (PPT and QST Heat) for the CTY-5339-A groups is equal to the corresponding onset time until a first responder event for CTY-5339-CB group will be tested against the alternative hypothesis that the event times are not equal.
- The null hypothesis that the duration time until the first non-responder event (QST and PPT) for the CTY-5339-A groups is equal to the corresponding duration time until the first non-responder event for CTY-5339-CB group will be tested against the alternative hypothesis that the event times are not equal.

The predicted outcome is that CTY-5339-A when locally applied to cheek mucosal tissue in the mouth will have an onset comparable to the fastest constituent, benzocaine, and a prolonged effect comparable to the longest acting constituent, tetracaine, of the combination product. The study also is designed to demonstrate that both the CTY-5339-A one and two-spray dosages are safe. (The assumption is made that benzocaine has a faster onset of action than tetracaine HCl.)

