13. STATISTICAL METHODS AND DATA HANDLING

The Statistics Group will perform statistical analyses of efficacy data. All computations will be performed using SAS® version 9.1 or higher (SAS Institute, Cary, NC). Statistical significance will be declared if the p-value is ≤ 0.05 .

Descriptive statistics for numerical variables will include n (number of subjects involved), mean, standard deviation, median, minimum, and maximum values. Categorical variables will be described by number and percent.

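### Fixed Bonferroni on the two primary endpoints is valid, but Holm at the same total alpha of 0.10 would make the second endpoint easier to claim

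*Combined protocol and SAP*

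**What the plan says.** Section 13.6 names two primary endpoints: "Duration of Effect, as assessed by PPT and QST Heat are co-primary efficacy parameters". It sets a familywise level of 0.10 and explains the choice: "since this is a proof of concept study, the total alpha level of 0.1 instead of 0.05 has been selected". The level is halved: "the total alpha level of 0.1 is Bonferroni adjusted to" 0.10/2, so each endpoint is tested at a fixed 0.05. The decision rule follows: "The study will be considered successful if either of the two primary endpoints is statistically significant".

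Three other places bear on the point.
- The opening of section 13 sets one threshold for the whole study: "Statistical significance will be declared if the p-value is" at or below 0.05. It makes no exception for the primary endpoints.
- Section 13.5 plans 95% confidence intervals.
- Section 8.4 makes the tests two-sided; the null hypothesis for duration, on both PPT and QST heat, "will be tested against the alternative hypothesis that the means are not equal".

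No stepwise procedure appears anywhere. Section 13.1 gives no power, effect size, standard deviation or correlation between the endpoints.

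**The concern.** Under fixed Bonferroni, the second endpoint must reach 0.05 whatever the first one shows. If the first endpoint has a real effect, only one true null hypothesis can remain. The plan then spends at most 5% of the 10% error it has allowed itself. Holm uses that unspent part: once the smaller p-value is at or below 0.05, the larger is compared with 0.10, and the familywise rate stays at 0.10.

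What is at stake is the formal claim on the second primary endpoint. A trial with pin prick at p = 0.02 and heat at p = 0.08 could claim only pin prick under 13.6 as written. Under Holm it could claim both. The information is limited: "The primary comparison of interest is one spray of CTY-5339-A compared to one spray of CTY-5339-CB", and "Each of the CTY-5339-A treatment regimens will have 38 exposures". A second p-value between 0.05 and 0.10 is therefore a realistic outcome.

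**Working it through.** **The plan's own figure.** 0.10 / 2 = 0.05, as stated. If the two tests were independent, the familywise error would be 1 − 0.95² = 0.0975, within 0.10.

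**Inputs from the plan.** Two endpoints, total alpha 0.10, two-sided tests, success if either is significant (sections 13.6 and 8.4).

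**Assumed inputs, because the documents give none.** Equal power w of 50% to 90% per endpoint at two-sided 0.05; correlation of the two test statistics 0 to 0.8; normal test statistics. The comparison does not depend on which test in section 13.5 yields the p-values.

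**Rules for claiming both endpoints.**
- Bonferroni: both p ≤ 0.05.
- Holm: smaller p ≤ 0.05 and larger p ≤ 0.10.

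Every pair of p-values that meets the first rule meets the second, so Holm cannot claim less.

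**Hand check at correlation 0.** Let w10 be the power of one endpoint at 0.10. Then P(both) is w² under Bonferroni and 2·w·w10 − w² under Holm, so the gain is 2·w·(w10 − w).
- w = 0.50: w10 = 0.624, gain 2 × 0.50 × 0.124 = 0.124.
- w = 0.70: w10 = 0.799, gain 2 × 0.70 × 0.099 = 0.139.
- w = 0.90: w10 = 0.945, gain 2 × 0.90 × 0.045 = 0.081.

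**Full grid.** Chance in % of claiming both, Bonferroni → Holm, from the bivariate normal distribution. The gain in points, in brackets, is taken before rounding.

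| Power per endpoint | corr. 0 | corr. 0.3 | corr. 0.5 | corr. 0.8 |
|---|---|---|---|---|
| 50% | 25 → 37 (12.4) | 30 → 42 (11.9) | 33 → 45 (11.5) | 40 → 50 (10.3) |
| 60% | 36 → 50 (13.8) | 41 → 53 (12.8) | 44 → 56 (12.0) | 50 → 61 (10.4) |
| 70% | 49 → 63 (13.9) | 53 → 65 (12.6) | 56 → 67 (11.6) | 61 → 71 (9.7) |
| 80% | 64 → 76 (12.2) | 67 → 78 (10.9) | 69 → 79 (10.0) | 73 → 81 (8.1) |
| 90% | 81 → 89 (8.1) | 82 → 89 (7.3) | 83 → 90 (6.7) | 86 → 91 (5.3) |

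The gain runs from 5.3 to 13.9 points. At 50% power and correlation 0.6 the figures are 35% → 46%.

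**Study success (at least one endpoint).** Both rules need the smaller p ≤ 0.05. The events are identical, so Holm's gain is exactly 0.

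**Familywise error with both nulls true.** 0.10 − P(both p ≤ 0.05), the same for both rules: 9.8%, 9.5%, 9.1% and 7.8% at correlation 0, 0.3, 0.5 and 0.8.

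**False claim on a null endpoint when only the other one works.** Bonferroni gives 5.0%. At correlation 0, Holm gives 0.05 + w × 0.05:
- w = 0.50: 7.5%.
- w = 0.80: 9.0%.
- w = 0.90: 9.5%.

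Positive correlation lowers this or leaves it unchanged (for example 8.6% at 80% power and correlation 0.5). It stays below 10% throughout.

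**The case against.** The strongest reply is that nothing in 13.6 is wrong. Bonferroni is valid, its 0.05 agrees with the threshold in section 13 and with the 95% intervals in 13.5, and the plan attaches no decision to winning on both endpoints. Section 13.1 treats significance as desirable and would accept a clear trend. All of this stands, and it is why the point is an optional refinement. It does not remove the gain: both endpoints are named primary and section 8.4 states the duration hypothesis for each, so the second claim has a place in the report.

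The cost objection also stands in part. Only the familywise rate is unchanged. The second endpoint could be claimed at p between 0.05 and 0.10, contrary to section 13 as now worded, and a matching 95% interval would then include no difference.

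Three stronger readings are tempting but unsupported.
- *Bonferroni reduces the chance of a successful study.* A reader might infer this from the word co-primary, which elsewhere often means that both endpoints must succeed. Section 13.6 says that either suffices, and on that rule Holm and Bonferroni are the same test.
- *The change costs nothing.* The higher false-claim rate on the second endpoint shows otherwise.
- *Hochberg would be better still.* It would add about 0.2 to 2.5 points to study success on the same grid. But it needs a condition on the dependence between the endpoints that the documents do not address, and it could declare success with both p-values between 0.05 and 0.10, so that neither meets section 13.

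**Conclusion.** The point holds as a cheap improvement. That Holm never rejects less than Bonferroni at the same familywise 0.10 is a mathematical fact and needs no assumption about power or dependence. The size of the gain, about 5 to 14 percentage points in the chance of claiming both endpoints, rests on assumed power and correlation and on equal power for the two endpoints. The gain is largest at moderate power and low correlation, and at most about 13 points if the correlation is 0.3 or more. Study success is unaffected. Whether the gain is worth a second-endpoint claim at p up to 0.10 is for the sponsor to judge. Since a total alpha of 0.10 has already been chosen for proof of concept, Holm only uses error that the plan has accepted.

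**What to change.** Make three short edits before the blind is broken.
- **Section 13.6:** replace the fixed split by Holm's procedure at total two-sided alpha 0.10. The smaller of the two primary p-values is compared with 0.05; if it is significant, the larger is compared with 0.10. The either-endpoint success rule stays as it is.
- **Section 13, opening paragraph:** add to the 0.05 threshold the words *except as specified in 13.6*.
- **Section 13.5:** state that the 95% intervals are descriptive for the second Holm step and are not its decision rule.

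Sample size, data collection and conduct do not change. The cost is the wording, plus accepting the higher false-claim rate on the second endpoint and a possible mismatch between its claim and its 95% interval. If the sponsor does not want a claim above 0.05 on any endpoint, the present text can stand.

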13.7 Safety Analysis

The safety population will consist of all subjects who received the study medication and had follow up data.

Adverse event (AE) analyses will include all AEs which initially occurred, or worsened following treatment (*i.e.*, treatment emergent signs and symptoms, TESS). AEs will be summarized by the MedDRA preferred term and by system organ class and classified according to their severity (mild, moderate, or severe) and relationship (“Suspect” or “Not Suspect”) to study medication. For the summary by severity, subjects who have multiple occurrences of the same AE will be classified according to the worst reported severity of the AE. Similarly, for the summary by relationship to the study medication, the AE will be classified according to the worst relationship.

ECG data will be summarized and presented based on assessment category (“Normal”, “Abnormal, but not clinically significant” or “Abnormal, clinically significant”) by treatment group. Changes in SBP, DBP, and methemoglobinemia rate from Baseline to 60 minutes will be summarized by treatment group. Pulse oximetry will be summarized at each time point by treatment group.

14. STUDY ADMINISTRATION

14.1 Investigator Study Binder

The Sponsor will supply to the PI an Investigator Study Binder that must be maintained at the study site, unless an alternative filing system is deemed appropriate by the Cetylite representative.

Included in this binder will be tabbed sections for maintaining the following: study identification and study site staff signature list, monitoring visit record, protocol and amendments/administrative changes, curricula vitae, Institutional Review Board documentation, informed consent form, product receipt and accountability forms, correspondence, subject screening record, and master subject log. This binder must be kept current and be available for review by representatives of the Sponsor and any official regulatory body.

14.2 Subject Identification

For purposes of confidentiality and to maintain anonymity, subjects will be assigned identification numbers. Subjects will be numbered sequentially as they enter the study. Once subjects meet the entry criteria, they will be assigned a randomization number corresponding to study medication. Subjects should be identified to the Sponsor only by their assigned number, initials and date of birth. The PI or his designee will maintain a complete list of all subjects enrolled in the study with their current mailing address on the master subject log. This list is necessary should contact of subjects be required in the future.

14.3 Case Report Forms

Case report forms (CRFs) provided by Cetylite will be used to document all subject data and will be typed or printed legibly in black or blue ink. Prior to submission to Cetylite the PI will review all CRFs and sign where necessary. It is important that the CRFs be completed in a timely manner for each subject evaluation in order that the progress and results of the study may be closely followed by the Sponsor. Corrections to CRFs must not obscure the original entry; a single line through the original entry is sufficient. All corrections must be initialed and dated by the responsible individual.

CRFs are to be completed and held for retrieval by a representative of Cetylite, unless otherwise directed. All study records must be retained in accordance with Section 14.10. A study site may use forms of their own design, following approval of the form by Cetylite, as source documents only.

14.4 Monitoring of Study

The study will be monitored by representatives of Cetylite. On-site visits will be made before the study begins, at regular intervals during the conduct of the study, and at the completion of the study. Communication by telephone, mail, and facsimile may also be used to supplement on-site visits.

The representative of Cetylite will inspect all CRFs and corresponding portions of the subject's original office and/or hospital records. These inspections are for the purpose of

verifying adherence to the protocol and determining the completeness and exactness of the data entered on the CRF and study medication log.

As a part of monitoring and inspection of this study, the PI agrees that Cetylite, its employees or representatives, Institutional Review Board or Independent Ethics Committee, as well as representatives of the FDA will have the right to inspect and review pertinent medical records relating to this trial. In addition, informed consent documents signed by study participants will indicate approval to release their medical records for review while maintaining their confidentiality.

14.5 Protocol Modifications

As the study progresses, any necessary additions or changes to the protocol will be decided by mutual agreement of the PI and the Clinical/Medical Monitor. An amendment to this effect will be submitted first to Cetylite for review and approval and then to the Institutional Review Board for review and approval prior to implementation. If the protocol change impacts the conduct of the study, the informed consent form will be amended, as appropriate. A protocol change to eliminate an apparent immediate hazard to subjects may be implemented immediately, provided the reviewing Institutional Review Board is notified in accordance with 21 CFR 56.104(c). Otherwise, no deviations will be permitted. Approved amendments will become part of the protocol and will be reported to the appropriate regulatory authority prior to implementation.

14.6 Discontinuation of Study by Sponsor or PI

Cetylite reserves the right to discontinue the study for administrative reasons at any time. All study medication and CRFs will then be returned to the Sponsor.

If the PI discontinues the study prematurely, the PI will return all study medication and CRFs to the Sponsor and provide a written explanation as to why the study was ended.

14.7 Disclosure of Data/Publications

All information obtained during the conduct of the study will be regarded as confidential. Agreement from Cetylite must be obtained prior to disclosing any information relative to the study.

Upon completion of the study, Cetylite may decide to publish the results with the PI in a recognized scientific journal and/or present the results (as a poster or oral presentation) at a meeting of a recognized scientific association. In order to safeguard against disclosure of confidential information, however, Cetylite requires that it has the right to review any manuscript and/or abstract prior to submission. A draft manuscript must be reviewed by Cetylite 60 days prior to submission of the final version to the journal. Abstracts of presentations must be reviewed by Cetylite 15 days prior to submission. Cetylite assures the PI that all manuscripts and abstracts will be reviewed promptly.

14.8 Informed Consent

Regulations require that written informed consent must be obtained for each subject prior to entry into the study. Informed consent means the knowing consent of an individual, so

situated so as to exercise free power of choice without undue inducement or constraint or coercion. The informed consent form will include all elements required by the FDA. A copy of the consent form will be provided to the subject.

The Investigator will provide Cetylite with a copy of the consent form as approved by the Institutional Review Board at University of Pennsylvania.

The PI will ensure that this study is in full conformance with the principles of the Declaration of Helsinki (as amended in Tokyo, Venice, Hong Kong South Africa and Scotland) as well as GCP and ICH guidelines.

14.9 Institutional Review

Prior to initiating the study, the protocol and amendments, informed consent form, any advertisement, PI's and sub-investigators' curriculum vitae, and investigational product brochure must be reviewed and approved by a properly constituted Institutional Review Board as required by the FDA and the International Conference on Harmonization Guidelines.

The PI must certify to Cetylite that the Institutional Review Board meets all the legal requirements as specified by the FDA. The Institutional Review Board must provide a signed and dated statement that the protocol, informed consent form, and other pertinent documents, such as recruitment advertisements (in any medium) have been approved by the Committee. If the study continues longer than one year, re-approval must be obtained from the Institutional Review Board on an annual basis. The Institutional Review Board must be informed of any changes in research activity including amendments to the protocol and/or informed consent form, advertisements, and serious adverse events.

At the conclusion of the study, the PI must submit a summary of the study to the Institutional Review Board with a copy forwarded to Cetylite no later than 60 days after the study closeout visit.

